### **7 STUDY OBJECTIVES**

#### **7.1 Primary Objectives**

- To assess the safety and tolerability of MOTREM in comparison with placebo, after single intravenous (i.v.) dose administration in healthy young male subjects.

#### **7.2 Secondary Objectives**

- To assess the pharmacokinetics of LR12 after single i.v. dose administration in healthy young male subjects
- To investigate the presence of anti-LR12 antibodies after single i.v. dose administration in healthy young male subjects

### **8 STUDY DESIGN**

#### **8.1 Overall Study Design and Procedure**

This will be a First in Human (FIH), randomised, placebo-controlled study, with sequential single ascending intravenous dose groups. Single doses of MOTREM (LR12) or matching placebo are planned to be administered following a sequential group design in 26 healthy young male subjects aged from 18 to 45 years.

This study incorporates the use of an adaptive design (8). Study specific adaptive features and their limits are described in Table 1.

Dose escalation and progression will be limited by evaluation of safety and tolerability data governed by toxicity rules (Section [8.3](#)) and will only occur after satisfactory review of all safety and tolerability data by the Safety Review Committee (Section [8.2.3](#)).

**Table 1. Adaptive Protocol Features.**

Adaptive Study Design Areas	Features	Limits
Dose	
 
1. All anticipated dose levels/dosing regimens in Parts A and B can be adjusted in accordance with PK, safety and tolerability data collected up to the decision making time-point.
 
2. In Part B, the anticipated dosing regimens can be adjusted in accordance with PK, safety and tolerability data collected up to the decision making time-point.
 
3. The term dosing regimen includes (1) the dose level administered as loading dose, (2) the dose level administered as maintenance dose (3) the duration of the loading dose and (4) the duration of the maintenance dose. Accordingly, these can be adjusted individually or in combination.
 
	
 
I. The starting dose for Part A of the study will not exceed 1 mg.
 
II. The maximum dose for Part A will not exceed 10 mg.
 
III. The starting loading dose in Part B will not exceed 0.5mg/kg.
 
IV. The starting maintenance dose in Part B will not exceed 0.03 mg/kg/h.
 
V. The dose increments between the dose levels 1 to 2 in Part A will be no more than 10-fold.
 
VI. The loading dose increments between the dose levels in Part B will be no more than 2.5-fold.
 
VII. The maintenance dose increments between the dose levels in Part B will be no more than 3.5-fold.
 

Timing	
 
4. Dosing regimens may overlap.
 
5. Cohorts/dosing regimens may be split into sub-groups
 
	
 
I. Protocol specific minimum study progression/escalation requirements for the SRC must be met before dose progression/escalation as described in section 8.2.
 
I. A mandatory sentinel dosing strategy of dosing one subject on IMP on the first day will be used for each cohort. If safety and tolerability is acceptable the remaining subjects of each cohort will be dosed in group sizes of no more than three with a minimum interval of 24 hours between the start of dosing in the first subject on the previous day and the start of dosing on the next day.
 
II. During a dosing day, there will be a minimum interval of 60 minutes between the start of (maintenance) dosing in a subject and the start of dosing in the next subject.
 
III. Additional sentinel or sequential dosing for all cohorts and study parts can be performed at the discretion of sponsor
 

Adaptive Study Design Areas	Features	Limits
Flexible Cohort Sizes	
6. Withdrawn subjects can be replaced at the discretion of the sponsor and investigator, if not withdrawn for safety reasons.
 
7. Replacement subjects may be enrolled in an ongoing cohort, or dosed together as a group or dosed separately.
 
8. The number of subjects in a dose cohort can be extended to gather further information on a dosing regimen.
	and investigator.
Optional Study Parts/Cohorts	9. Optional groups/cohorts may be included to explore additional dose levels and/or dosing regimen.	
I. The maximum extension is 100% of the original group/cohort size at the selected dose level.
 
II. The randomisation will follow the randomisation system of the originally planned dose cohort.
 
III. Study specific toxicity rules (Table 4) apply.

Samples and Assessments	
10. The in-house stay or follow-up period may be prolonged if:
 
 
a. It is considered clinically necessary by the PI or delegate for individuals on a case-by-case basis.
 
b. The Safety Review Committee (SRC) considers it necessary from a safety/tolerability point for an upcoming dose group/cohort.
 
c. The follow-up period for a dose cohort may be prolonged if evolving PK data require a longer follow-up period.
 
	
I. A maximum extended in-house or follow-up period cannot be defined as the extension will be as long as necessary to ensure the safety of the individual participant(s).
 
II. The maximum extended in-house or follow-up period for study cohorts will be based on evolving safety, tolerability and PK data and will not usually exceed <math>10 \times t_{1/2}</math> of the IMP following the last dose.
 
III. Extension of in-house or follow-up period does not constitute an SAE, unless a subject is hospitalised as patient of the National Health Service or the AE meets other SAE criteria.

	
11. Additional safety blood and/or urine samples/variables may be taken or analysed if:
 
 
a. It is considered clinically necessary by the PI or delegate for individuals on a case-by-case basis.
 
b. The SRC considers it necessary from a safety/tolerability point for an upcoming dose cohort.
 
	
I. For individuals, a maximum number of safety blood samples will be determined on a case-by-case basis and cannot be pre-defined as investigations will be performed as necessary to ensure the safety of the individual participants.
 
II. For dose cohorts, study specific maximum blood volumes will not be exceeded (see section 12.7).

	
12. Timing of PK and/or immunogenicity samples may be adjusted in accordance with evolving data and dosing schedule.
 
13. Additional or less PK and/or immunogenicity samples may be taken in accordance with evolving data and dosing schedule.
	
I. Minimum: sufficient PK samples to establish full protocol specific serum PK profile. Sufficient immunogenicity samples to enable evaluation of de novo antibody development.
 
II. Study specific maximum blood volume will not be exceeded (see section 12.7).

	14. Timing of safety assessments including but not limited to laboratory safety samples, vital	I. Alterations in timing of the safety assessments need to be a reflection of the established PK, safety and

Adaptive Study Design Areas	Features	Limits
	signs and ECGs may be adjusted in accordance with evolving data and dosing schedule.  15. Additional safety assessments including but not limited to laboratory safety samples, vital signs and ECGs may be taken in accordance with evolving data and dosing regimens.	tolerability profile up to the decision making time-point.  II. Alterations need to be made in the spirit of the current CSP (i.e. focus on the capture of essential and useful data) and not affect the risk profile of the study.
	16. Specialist referrals (e.g. to a cardiologist) may be made (and may include all relevant assessments and investigations) if it is considered clinically necessary by the PI or delegate or Sponsor or SRC for individuals on a case-by-case basis.	I. A maximum for individuals will be determined on a case-by-case basis and cannot be pre-defined as investigations will be performed as necessary to ensure the safety of the individual participants.
	17. Except for those subjects that have been randomised, screening assessments, including Holter ECG recordings performed at Richmond Pharmacology Ltd on volunteers screened for another study can be used for this study to avoid unnecessary tests.	I. The assessments must meet protocol criteria (e.g. the method to be used) II. The assessments must be performed within the protocol defined screening window III. The Holter ECG recordings are valid for a period of three months.
AEs	18. Allow for the study to continue under the originally approved CSP and IMPD in case of new pre-clinical or clinical findings.	I. Applicable only for findings which do not affect the risk profile or objectives of the study.

## Study Plan

Single doses of MOTREM (LR12) or matching placebo (Part B) are planned to be administered following a sequential group design in 26 healthy young male subjects aged from 18 to 45 years: Part A (Groups 1 and 2 of 1 subject each) followed by Part B (Groups 3 to 8 of 4 subjects each). For Part A (Groups 1 and 2), one subject each will receive MOTREM. For Part B (Groups 3 to 8) 3 subjects will receive MOTREM and 1 subject will receive placebo (3:1 ratio). Dose escalation to the following scheduled dose will only occur after satisfactory review of all safety and tolerability data by the Safety Review Committee in accordance with Table 1, protocol sections [8.2](#) Rules for dose escalation/progression and [8.3](#) Toxicity rules.

Subjects will be screened within 14 days and may be performed over multiple days prior to entering the study on Day -1. Each subject will receive verbal and written information followed by signing of the Informed Consent Form (ICF) prior to any screening procedures taking place. Subjects will be admitted on Day -1 and on Day 1 of the study each subject will receive MOTREM (LR12). All the subjects from Part A (Groups 1 and 2) and Part B (groups 3 to 8) will be discharged on Day 2 after 24h post-dose (start of infusion). They will attend the unit for a follow-up visit on Day 8±1. The End of Study visit will take place on Day 28±2. All the assessments performed during the study are detailed in the Study Plan (Table 2 and Table 3). Study design features as well as number of subjects may be adapted according to Table 1.

The end of study is defined as the last subject, last visit (LSLV).

[figure not shown]

Figure 1: Study Flow Chart.

**Table 2. Study Plan – Part A (Groups 1 and 2).**

Groups 1 and 2	Screening		Assessment Period										FU Visit D8±1	EOS Visit D28±2		
	D-14 to D-2	D-1	D1													
			Predose	H0	H1	H2	H3	H4	H5	H6	H7	H8				
SCREENING PROCEDURES																
Signature of the informed consent	X															
Medical history	X	X														
Prior medications	X	X														
Physical examination	X	X 											X 	X 		
Viral Serology	X															
Alcohol breath test & Urine Drug Screen	X	X														
Inclusion / exclusion criteria	X	X														
Randomisation				X												
24h Holter	X															
Hospitalisation																
Study treatment schedule				T0' to T15'												
Meals 		X				X										
SAFETY ASSESSMENTS																
Vital signs  (including BMI assessment at screening)	X	X	X	T0', T10', T20, T30, T40, T50'	X	X	X	X	X	X	X	X	X	X		
ECG	X	X	X	T15'	X	X							X			
Telemetry 					←							→				
Haematology	X	X		T15'			X						X			
Coagulation	X	X		T15'			X						X			
Serum chemistry	X	X		T15'			X						X			
Urinalysis	X	X											X			
Infusion site assessment			X	T15' 	X		X						X			
Anti-LR12 antibody screening 			X										X	X		
Pharmacokinetics			X	T15'	X											
Adverse Events	←												→			
Concomitant medication	←												→			

(1) Brief physical examination.

(2) Standard meals will be served at standard times. Meal at dismissal will be optional.

(3) Time of procedures is relative to the start of infusion.

(4) Tympanic temperature will be collected at predose and at H8 only. Vital signs at H0 will be measured only in supine position.

(5) 12-Lead telemetry will be recorded from pre-dose to 10 h post-dose.

(6) The check of the local tolerability at H0 should be performed just after the loading infusion

(7) Should any subject develop ADA against LR12, they will be followed up for at least 3 months or until the antibody response is no longer detected.

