**Anticipated Duration of Treatment:**

Single dose administration.

Part A (Groups 1 and 2): 15 minutes i.v. dose

Part B (Groups 3 to 8): 7 hours and 45 minutes continuous i.v. administration after a 15 minutes i.v. loading dose.

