#### **6.4.2 Potential Risks**

##### **6.4.2.1 Nonclinical Safety Pharmacology and Toxicology:**

Toxicity studies were only conducted in one species in accordance with ICH guidance documents S6(R1) and M3(R2) as well as to EMA’s guidance on repeated dose toxicity (EMEA/CHMP/SWP/488313/2007). Safety pharmacology also followed the ICH S7A and S7B guidance.

A cardiovascular safety study in Cynomolgus monkeys did not identify any adverse cardio-vascular effect of LR12, when administered as an intravenous infusion of 18-times the expected pharmacologically active dose. In addition, the central nervous and pulmonary systems were explored during the toxicity studies and did not unveil untoward effects.

Receptor binding assays with a wide range of receptors did not show any relevant off target effects in vitro.

A bacterial reverse mutation test (Ames test) and a chromosome aberration test did not show any evidence for genotoxicity of LR12.

Toxicokinetic studies showed dose-dependent kinetics and suggested a clearance of the product within 15 to 30 minutes depending on the dose.

A series of toxicity studies was conducted with LR12 in cynomolgus monkey, as this represents the only relevant species. In the pivotal 14-day toxicology study with the clinical formulation, the administration of LR12 was safe and well tolerated at doses 7.2, 24 and 140 mg/kg/day. No adverse events were observed up to the highest dose level. In addition, a dose of 440 mg/kg/day in a preliminary formulation was found to be safe and well tolerated in a 14-day study.

Severe time dependent adverse events, likely related to immunogenicity, were observed in the low- dose arm of an early toxicity study conducted with an experimental frozen formulation that was diluted with a technical, non USP grade buffer. Further toxicology studies with a suitable buffer or the API alone and with the final clinical formulation did not reproduce these findings.

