#### **6.4.2.3 Allergic Reactions, Infusion Reactions and Anaphylaxis**

As with all protein products, administration of MOTREM may result in hypersensitivity reactions including anaphylaxis, or infusion site associated reactions.

Subjects will be closely monitored during and after IMP administration for any symptoms of anaphylaxis and other hypersensitivity reactions, including circulatory and/or respiratory changes or arrest, or urticaria, arthralgia, myalgia or other signs of related reactions. Adequate treatment will be immediately available. Infusion-associated AEs may occur, and depending on its type and severity, discontinuation of infusion may be required. Subjects will be informed of early symptoms and signs of hypersensitivity reactions including hives, swollen face, eyelids, lips, or tongue, or trouble with breathing. An acute infusion reaction algorithm will be used to manage infusion related reactions (refer to Appendix [19.2](#)). In this study regular assessments to monitor infusion reactions and infusion site reactions will be done.. A mandatory sentinel dosing strategy of dosing one subject on IMP on the first day will be used

for each cohort. If safety and tolerability is acceptable the remaining subjects of each cohort will be dosed in group sizes of no more than three with a minimum interval of 24 hours between the start of dosing in the first subject on the previous day and the start of dosing on the next day. In addition, during a dosing day, there will be a minimum interval of 60 minutes between the start of (maintenance) dosing in a subject and the start of dosing in the next subject to ensure that reactions can be dealt with promptly. Any reactions will be treated and taken into account in the dose progression/escalation and toxicity rules. If anaphylactic reactions occur the current “UK Treatment Guideline for Anaphylactic Reactions” of the UK Resuscitation Council will be followed (refer to Appendix [19.1](#)).

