**Table 3. Study Plan – Part B (Groups 3 to 8).**

Groups 3 to 8	Screening		Assessment Period												FU Visit	EOS Visit
	D-14 to D-2	D-1	Predose	H0	H1	H2	H3	H4	H5	H6	H7	H8	H10	H24		
	D1												D2	D8±1	D28±2	
SCREENING PROCEDURES																
Signature of the informed consent	X															
Medical history	X	X														
Prior medications	X	X														
Physical examination	X	X 												X 	X 	X 
Viral Serology	X															
Alcohol breath test & Urine Drug Screen	X	X														
Inclusion / exclusion criteria	X	X														
Randomisation				X												
24h Holter	X															
Hospitalisation																
Study treatment schedule				i.v. loading dose T0 to T15'												
Meals 		X										X			X	
SAFETY ASSESSMENTS																
Vital signs  (including BMI assessment at screening)	X	X	X	T0', T10', T20, T30, T40, T50'	X	X	X	X	X	X	X	X	X	X	X	X
ECG	X	X	X	T15'	X								X	X	X	
Telemetry 			X													
Haematology	X	X		T15'				X							X	
Coagulation	X	X		T15'				X							X	
Serum chemistry	X	X		T15'				X							X	
Urinalysis	X	X													X	
Infusion site assessment			X	T15' (6)	X	X		X		X		X			X	
Anti-LR12 antibody screening 			X												X	X
Pharmacokinetics 			X	T5', T15', T18', T30', T45'	X	X		X		X			T-15, T2', T4', T7', T15', T30	X		
Adverse Events	←														→	
Concomitant medication	←														→	

(1) Brief physical examination.

(2) Standard meals will be served at standard times. Meal at dismissal will be optional.

(3) Time of procedures is relative to the start of infusion.

(4) Tympanic temperature will be collected at pre-dose and at H8 only. Vital signs at H0 and H8 will be measured only in supine position.

(5) 12-Lead telemetry will be recorded from pre-dose to 10 h post-dose.

(6) The check of the local tolerability at H0 should be performed just after the loading infusion.

(7) PK sampling performed at the end of the 8 hours i.v. infusion will be as follows: 15 min before H8 (T-15'), then during 30 min after the end of the infusion as specified in the table. H0 timings refer to start of infusion.

---

(8) Should any subject develop ADA against LR12, they will be followed up for at least 3 months or until the antibody response is no longer detected.

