#### Safety:

- AEs
- Vital sign variables (temperature, blood pressure, heart rate)
- ECGs variables (12-lead ECG, telemetry and Holter)
- Clinical laboratory variables (haematology, coagulation, biochemistry, urinalysis)

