#### Vital signs, ECG, physical examination and laboratory data:

Vital signs (SBP, DBP, heart rate, T°), ECG, physical examination and laboratory data will be described at each visit/time. Changes from baseline will be described. Abnormal values will be identified in subject data listings.

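### Tympanic temperature is scheduled only pre-dose and at H8, leaving the infusion period and the 16 h up to the Safety Review Committee's 24 h data point without a scheduled reading

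*Combined protocol and SAP*

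**What the plan says.** Footnote 4 to the vital-signs row sets the temperature schedule in both study plans. Table 2 (Part A) reads "Tympanic temperature will be collected at predose and at H8 only" and Table 3 (Part B) reads "Tympanic temperature will be collected at pre-dose and at H8 only". Footnote 3 of Table 2 fixes the clock: "Time of procedures is relative to the start of infusion".

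The vital-signs row itself is much denser. It has six sets in the first hour (T0' to T50') and hourly sets from H1 to H8. Part B also has sets at H10 and H24. Section 12.2.1 ties these time points to blood pressure and heart rate. For temperature it names the thermometer but gives no times.

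Temperature is used in several other places:

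- Section 8.2.2 lists it in the safety data for the SRC: "Vital sign variables (temperature, blood pressure, heart rate".
- Section 8.2.4 sets the SRC's minimum window at 24 h from the start of infusion.
- Section 8.4.4 requires the T+50 min vital signs to be reviewed before the next subject is dosed.
- Section 13.1.2 includes tympanic temperature among the findings that become adverse events if they deteriorate, in a clinically relevant way, from screening values.
- Section 15.1.3 says: "Vital signs (SBP, DBP, heart rate, T°), ECG, physical examination and laboratory data will be described at each visit/time".

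**The concern.** This is a first-in-human infusion study whose primary objective is safety and tolerability. Followed exactly, the footnote gives each subject one temperature before dosing and one at H8. A rise that starts and settles before H8, or starts after it, would be recorded only if someone had a reason to take an unscheduled reading. The pre-dose/H8 pair could then look unchanged, and a reader of the SRC report or the final tables could mistake this for evidence from monitoring throughout the infusion.

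The footnote also leaves two other parts of the protocol without a value they appear to need: the adverse-event definition, which compares with screening, and the T+50 min check between subjects.

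**Working it through.** The plan gives no figure of its own to reproduce. The check is interval arithmetic on the schedule, followed by a comparison of sections.

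**Inputs**

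- Temperature times: pre-dose and H8 (Tables 2 and 3, footnote 4).
- Clock: time 0 is the start of infusion (footnote 3).
- Part A infusion: "Part A (Groups 1 and 2): 15 minutes i.v. dose" (Synopsis), so 0.25 h.
- Part B infusion: 15 min loading plus 7 h 45 min maintenance (Synopsis), so 0.25 h and 7.75 h.
- SRC minimum window: 24 h from start of infusion (Section 8.2.4).

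**Intervals without a scheduled temperature**

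1. Part A, end of infusion to first post-dose reading: 8 − 0.25 = 7.75 h, that is 7 h 45 min.
2. Part B, infusion length: 0.25 + 7.75 = 8.0 h. H8 is therefore the end of the infusion, and the interval from its start to its end has no scheduled reading.
3. Both parts, H8 to the SRC's 24 h point: 24 − 8 = 16 h.

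**Vital-sign sets without temperature, Part B**

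- From T0' to H7: 6 + 7 = 13 sets, none with temperature.
- From T0' to H24: 6 (first hour) + 8 (H1 to H8) + 1 (H10) + 1 (H24) = 16 sets, one with temperature.

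I give no matching total for Part A, because the columns of Table 2 after H8 cannot be read reliably in the available text. The word 'only' excludes a 24 h temperature whatever those columns contain.

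**Footnote 4 against the sections that use temperature**

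| Section | What it needs | What footnote 4 supplies | Result |
|---|---|---|---|
| 13.1.2 | A screening temperature for comparison | Pre-dose and H8 only | Inconsistent on a literal reading |
| 8.4.4 | Vital signs at T+50 min before the next subject is dosed | No temperature at T+50 min | Inconsistent if vital signs include temperature |
| 8.2.2 | Temperature among the SRC's variables | Two values per subject | Met, with thin coverage |
| 15.1.3 | Description at scheduled times and change from baseline | Two values per subject | Met |

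On Section 8.4.4, the protocol uses the term vital signs in two ways. Section 8.2.2 and the Synopsis include temperature, whereas Section 12.2.1 equates the term with blood pressure and heart rate when it refers to the time points.

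**The case against.** The best defence is that temperature is one signal among many. Blood pressure and heart rate are taken frequently, telemetry runs to 10 h, infusion sites are checked repeatedly, and adverse events are observed and elicited. Feature 15 in Table 1 allows additional vital signs. Section 6.4.2.3 promises that "In this study regular assessments to monitor infusion reactions and infusion site reactions will be done", and those assessments do exist. All of this stands, and it limits the point to scheduled coverage. It does not close the gap: feature 15 is optional and depends on evolving data, and readings prompted by symptoms do not replace a reading taken on every subject at the same times.

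It can also be argued that footnote 4 governs Day 1 only, so that screening, Day -1 and Day 2 temperatures would be taken. The text does not say so. If that is the intention, the Section 13.1.2 mismatch disappears and H24 is covered in Part B, but the gap from T0' to H8 remains.

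A reader might infer more than the documents support:

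- **That the SRC list in Section 8.2.2 is contradicted.** Listing a variable sets no frequency. Holter is on the same list and is scheduled only at screening.
- **That Section 15.1.3 is contradicted.** The same sentence covers ECG, physical examination and laboratory data, none of which is taken at every time point. It means each scheduled time, and a change from pre-dose to H8 can be calculated.
- **That the Part A delay should be scaled by drug clearance.** Section 6.4.2.1 says that toxicokinetic studies "suggested a clearance of the product within 15 to 30 minutes depending on the dose", but nothing in the documents says that a temperature response follows plasma concentration.
- **That fever is a leading expected risk.** Neither the signs in Section 6.4.2.3 nor the graded categories in Section 8.3 name it.
- **That the comparison with placebo is biased.** Part A has no placebo, and in Part B both arms follow the same schedule.

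**Conclusion.** The point holds as a coverage gap and two inconsistencies. After dosing starts, one temperature is scheduled per subject in the 24 h that the SRC reviews. Part A has none in the first 7 h 45 min after its infusion ends, Part B has none between the start and end of its 8 h infusion, and both have none from H8 to 24 h. Section 13.1.2 refers to a screening temperature that the footnote does not provide, and the T+50 min check in Section 8.4.4 contains no temperature.

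This rests on reading 'only' literally and concerns scheduled readings. The Study Operations Manual and the content of the infusion-reaction algorithm (Appendix 19.2) are not available here, and either could call for further readings. The documents do not allow an estimate of how often a transient rise would be missed. The change is a cheap improvement to safety data; the gap does not invalidate the SRC process or the planned safety analysis.

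**What to change.** In footnote 4 of Tables 2 and 3, remove the restriction to pre-dose and H8, so that tympanic temperature is taken with vital-sign sets already scheduled. These should include screening and Day -1, sets during and soon after the infusion, and H10 and H24 where scheduled.

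Reconcile the footnote with two sections. Section 13.1.2 should name a baseline temperature that is actually collected. Section 8.4.4 should say whether its T+50 min check includes temperature, and the schedule should agree with the answer.

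No new visit or blood sample is needed. The cost is a few seconds per set and some extra data entry. From T0' to H24 in Part B this is at most 16 − 1 = 15 further readings per subject, plus two before dosing (screening and Day -1), and fewer if some first-hour sets are left out. Whether the change counts as a non-substantial amendment is for the sponsor to confirm. If the present schedule is kept, the SRC reports and safety tables should state that temperature was scheduled only at pre-dose and H8.
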